12. INFORMED CONSENT

Process To Be Followed For Obtaining Consent/Accent/Permission And HIPAA Authorization.

We request a waiver of documented consent for conducting the phone screening. This part of the research, i.e., the telephone interview, presents no more than minimal risk of harm to subjects and involves no procedures for which written consent is normally required outside of the research context. If a subject qualifies for the study and decides to participate, the screening information will be kept with their research record. If they not qualify for the study, the screening information will be destroyed.

1. Potentials volunteers will be screened via telephone interview (Appendix 16) and, as appropriate, via face-to-face assessment. Telephone screening (respondents blind to selection criteria) will assure volunteers meet general age and medical criteria. For those subjects interested in proceeding to a face-to-face assessment, a consent form will be mailed with instructions to peruse the document. The intent of this is to allow sufficient time for the prospective participant to consider whether to participate; a step to be taken to minimize the possibility of coercion or undue influence.
2. The Research Associate will obtain consent /authorization. The person in this position will undergo CITI training to gain requisite knowledge to perform the consent /authorization process. S/he will have sufficient knowledge of the study to answer any questions regarding the study. S/he will explain the research activity, how it is experimental (e.g., a new drug, extra tests, separate research records, or nonstandard means of management, such as flipping a coin for random assignment or other design issues). S/he will inform the human subjects of the reasonably foreseeable harms, discomforts, inconvenience and risks that are associated with the research activity. Information communicated to the participant/parent or legally authorized representative during the consent/assent/permission process will not include exculpatory language through which the participant is made to waive or appear to waive any of the participant's legal rights or release or appear to release the Researcher, Sponsor, the University or its agents from liability for negligence.
3. The Investigator will retain the original consent form and HIPAA authorization in a master research file. An electronic copy of the signed informed consent and HIPAA authorization will also be inserted into the electronic Medical Record alerting other providers of the subject's participation in this research protocol.

13. ALTERNATIVES TO STUDY PARTICIPATION

The therapeutic alternatives that are reasonably available that may be of benefit to a potential participant include standard of care measures; e.g., spinal manipulation, acupuncture, biofeedback, cognitive-behavioral therapy, massage and/or a comprehensive rehabilitation programs.

In a study such as the present one where there is no prospect of direct benefit to the participant, another alternative is to note participate.

14. POTENTIAL RISKS

Likely

- difficulties with balance
- eye irritation
- throat irritation
- increased heart rate
- possible low blood pressure
- reversible problems with your appetite, lethargy

Less Likely

- some change in your mood (good or bad)
- loss of memory
- decreased ability to concentrate or think properly

Rare But Serious

- dizziness
- head and chest pressure
- disorientation
- agitation
- combativeness
- incoherence
- visual hallucinations

Physical harm: Risks of inhaled cannabis products may include psychomotor coordination difficulties, eye irritation, throat irritation, increased heart rate, possible hypotension, and reversible appetite/mood/memory/cognition effects.

There may be some discomfort when blood samples are taken, and there is a small risk of bruising, infection, or inflammation at the site at which the needle is inserted. We will be taking two tablespoons of blood for the purposes of this study.

There is virtually no risk associated with pain testing in cold water unless there is a circulatory problem. The subject will be free to withdraw their hand from the water bath at any time. However, there is always the possibility of damage despite these precautionary measures.

- **Psychological harm:** Mental and/or emotional distress may result from questions asked during assessment or as a result of the time taken in the assessment process. Additionally, some neuropsychological tests may require concentrated effort and may be frustrating for the subject to complete.
- **Legal harm:** We will be asking sensitive questions about use of marijuana, and testing for illicit substance use. Access to such material for legitimate research purposes is generally acceptable, as long as the researcher protects the confidentiality of that information.
- **Social harm:** Invasions of privacy and breaches of confidentiality may result in embarrassment within one's business or social group. Every effort will be made to maintain confidentiality of the subject's participation to lessen this type of risk. Subjects may have some discomfort or feel embarrassed when they provide a stool sample.

- **Economic harm:** Eligibility for insurance, political campaigns, and standing in the community are problems may result from loss of confidentiality. Vaporizing marijuana may hinder application for future employment, if drug screening is a condition of employment. It is likely that detectable traces of marijuana will remain in the subject's hair or blood for a minimum of six weeks after vaporizing. If applicable, a letter will be written to the subject's employer explaining their participation in this research study and the dates of participation. Confidential information regarding your history, DNA information (genetic risk for certain diseases), substance use or health diagnosis may become known outside of the research setting.
- **Reproductive risks:** The procedures in this research are known to hurt a pregnancy or fetus in the following ways: poor educational attainment. A participant should not become pregnant or father a baby while on this study because the drugs in this study can affect an unborn baby. Women should not breastfeed a baby while on this study. Subjects will need to use birth control while on this study. Acceptable methods of birth control are: oral contraceptive pills, diaphragm and condom with spermicide, progestin implant, intrauterine contraceptive device.
- **Unknown Risks:** The experimental treatments may have side effects that no one knows about yet. The researchers will let subjects know if they learn anything that might make you change your mind about participating in the study.

15. RISK MANAGEMENT PROCEDURES AND ADEQUACY OF RESOURCES

At every study visit, stopping criteria will include:

Pulse: an irregular pulse or pulse rate > 110 beats per minute

Blood Pressure: systolic blood pressure > 180 mmHg or diastolic > 110 mmHg

Respirations: respiratory rate > 20 breaths per minute

Pulse: an irregular pulse or pulse rate greater than 110 beats per minute will result in cessation of participation and, if deemed advisable by a study clinician, transfer to the emergency department (across the street from our research center).

Blood Pressure: If the systolic blood pressure is ≥ 160 to < 180 mmHg or the diastolic is ≥ 100 to < 110 mmHg, a study clinician will conduct an evaluation to see if the participant has symptoms that would mandate discontinuation. Examples would include severe headache, confusion, chest pain, dyspnea, irregular heartbeat, and/or palpitations. Final determination regarding possible discontinuation will be made by a study investigator. If discontinued from the study, the participant will be asked to have their blood pressure evaluated by their primary care physician as soon as possible. If the systolic blood pressure is > 180 mmHg or the diastolic is > 110 mmHg, the participant will be discontinued from the study and either be transferred to the emergency department or be asked to visit their primary care physician as soon as possible. The end organ response to the blood pressure will guide the clinician's decision (e.g., the development of angina pectoris or hemiplegia will mandate transfer to the emergency department).

Respirations: shortness of breath will result in potential cessation of participation and possible transfer to the emergency department following evaluation by a study clinician, who will consult with the study investigator.

A locally developed self-report instrument, the Cannabis Solicited Adverse Events (Appendix 29) will be administered to assess distress from psychological effects of cannabis. This will be performed on a prn basis by the trained staff and routinely at the end of the acute

administration session. The items on this instrument ask participants about experiencing anxiety, paranoia, and hallucinations. Excess intoxication will also be assessed using this instrument which asks participants about their having dizziness, drowsiness, confusion, emotional changes, and/or cognitive changes. Positive responses to these items, if Grade 2, 3 or 4 (see below for definitions), will result in notification of a study clinician who will speak with the participant to see if discontinuation of participation in the study would be in her or his best interest.

Using the Cannabis Solicited Adverse Events instrument mentioned above, an Adverse Events Form (Appendix 30) will be completed. Adverse events will be characterized as 1 = Mild, 2 = Moderate, 3 = Severe, and 4 = Life Threatening using the following definitions (consistent with those used by the National Cancer Institute):

GRADE 1 MILD	GRADE 2 MODERATE	GRADE 3 SEVERE	GRADE 4 POTENTIALLY LIFE-THREATENING
Mild symptoms causing no or minimal interference with usual social & functional activities with intervention not indicated	Moderate symptoms causing greater than minimal interference with usual social & functional activities with intervention indicated	Severe symptoms causing inability to perform usual social & functional activities with intervention or hospitalization indicated	Potentially life-threatening symptoms causing inability to perform basic self-care functions with intervention indicated to prevent permanent impairment, persistent disability, or death

Inasmuch as the scoring of Grades 2, 3, and 4 mention that an intervention is indicated, AEs with Grades 2 or 3 will be brought to the attention of a study clinician so that s/he may interact with the participant to determine if discontinuation of study participation is warranted. This will be done in consultation with an investigator. Grade 4 AEs will be managed by reports tendered to the FDA and the IRB within the required time limits specified by each organization. There will also be a determination of whether the AE is related, possibly related or not related to the study by the investigator for Grades 1 to 4.

Furthermore, the participant will be followed by the research team to insure that the AE(s) resolve. This might include recommending that the participant see their primary care physician (e.g., for a change in blood pressure medication).

Risks will also be mitigated using the following measures:

- Preventing children and adolescents from gaining access to medicinal cannabis because of potential harm to their well-being. Subjects will be required to store cannabis in an area of their home that would prevent anyone else from discovering its location.
- Because some people cannot control their use of cannabis, we will not allow patients with recent substance abuse histories (less than 12 months) to participate.
- We will exclude patients if they are pregnant or refuse to exercise birth control if engaging in sexual activities that could result in pregnancy, have a heart disease or heart rhythm problem or have a history of serious mental illness (e.g., schizophrenia, mania, or a history of hallucinations or delusions)
- In order to avoid carcinogens, we will have subjects use a vaporizer rather than smoke joints or use a water pipe.

- We will instruct subjects not to drive a car or operate heavy machinery for 3-4 hours after use of medicinal cannabis, or longer if larger doses are used or the effects of impairment persist. They will use a designated driver for automobile transportation if they have to go out sooner than 3-4 hours after taking this medicine.
- As the response to cannabis varies widely, participants will titrate to effect and in essence use the minimum amount of medicinal cannabis needed to obtain relief from pain.
- A cannabis withdrawal syndrome will be under surveillance for two weeks; difficulty with getting to sleep and angry outbursts might require that they withdraw from the cannabis more slowly.

The UCSD Department of Psychiatry (Appendix 17) is committed to providing the resources and other supports (e.g., data management and information systems, statistical, and physical performance site) to ensure the timely implementation, conduct, and completion of this program.

Data and Safety Monitoring Board (DSMB)

A DSMB will be selected utilizing a group of experts that will advise the study investigators, with the primary responsibility to monitor human subject safety. The members will be comprised of at least 3 independent clinicians familiar with the conduct of clinical trials. The DSMB will consider study-specific data as well as relevant background information about the test agents and target population under study. The DSMB will review the protocol, including the safety monitoring plan, and identify any major concerns prior to implementation. During the trial the DSMB will review:

1. Real-time and cumulative safety data for evidence of study-related adverse events, unanticipated problems
2. Factors that might affect the study outcome or compromise the trial data (such as protocol violations, losses to follow-up)
3. Staff performance for protection of privacy, confidentiality, and maintenance of secured databases
4. Progress of interventional trial, including periodic assessments of data quality and timeliness, participant recruitment, accrual and retention.

The DSMB should conclude each review with each member's recommendation as to whether the study should continue or be modified. Recommendations for modification of the design and conduct of the study may include corrective action when performance is unsatisfactory. Confidentiality must always be maintained during all phases of DSMB review and deliberations. The DSMB report will include the participants' demographic characteristics, expected versus actual recruitment rates, treatment retention rates, any quality assurance or regulatory issues that occurred during the past year, a summary of all and serious adverse events, and any actions or changes with respect to the protocol.

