- Presence of another painful condition of greater severity than the back pain condition which is being studied.
- History of traumatic brain injury.
- Clinically significant or unstable medical condition. Individuals with significant cardiovascular, hepatic or renal disease, uncontrolled hypertension, and chronic pulmonary disease (eg, asthma, COPD), will be excluded. With respect to cardiovascular and pulmonary status, a clinician will screen participants with a tool developed for detection of congestive heart failure, coronary artery disease, obstructive and/or restrictive lung disease (Appendix 28 Cardiopulmonary Screen). Hepatic and renal disease will be evaluated with liver and renal function laboratory tests. If warranted clinically, subjects will undergo further evaluation (urinalysis, electrocardiogram, and/or chest X-ray).
- A positive result on toxicity screening will exclude individuals from participation. A urine drug test that screens for 5 categories of drugs: marijuana ($\Delta 9$ -THC), cocaine, amphetamines/methamphetamines, opiates, benzodiazepines and phencyclidine (PCP) will be employed. A positive result for opioids and/or THC will not be exclusionary if the patient is receiving a prescription for an opioid and/or THC.
- Allergy to sesame oil, lactose, or gelatin
- Vascular disease, especially Raynauld's syndrome, systolic blood pressure > 170 mm, diastolic blood pressure > 100 mm
- Recent injuries to the upper extremity
- Cognitive impairment, such as Dementia or Alzheimer's Disease
- Substance Abuse History: individuals with current substance use disorders⁵⁵ as assessed using the Drug Abuse Screening Test (DAST-10) (a score greater than or equal to 3) and the Alcohol Use Disorders Identification Test (AUDIT) (a score greater than or equal to 8 or a score greater than or equal to 7 if over 65 years old) (Appendix 31).
- Pregnancy as ascertained by a mandatory commercial pregnancy test
- Women who are lactating

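### The blood-pressure rules in Protocol Section 15 leave a gap at systolic 180 and diastolic 110: 180/90 has no stated action, although 179/90 is evaluated and 181/90 is stopped

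*Protocol*

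**What the plan says.** Protocol Section 15 opens with stopping criteria that apply at every study visit. The blood-pressure entry is "Blood Pressure: systolic blood pressure > 180 mmHg or diastolic > 110 mmHg".

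The paragraph that follows sets two tiers:

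- **Evaluation.** "If the systolic blood pressure is ≥ 160 to < 180 mmHg or the diastolic is ≥ 100 to < 110 mmHg", a study clinician looks for symptoms that would require discontinuation. "Final determination regarding possible discontinuation will be made by a study investigator".
- **Discontinuation.** "If the systolic blood pressure is > 180 mmHg or the diastolic is > 110 mmHg, the participant will be discontinued from the study", with transfer to the emergency department or referral to primary care.

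The only other numeric blood-pressure limit is the exclusion criterion in Protocol Section 10, "systolic blood pressure > 170 mm, diastolic blood pressure > 100 mm", which governs entry and not conduct on study. The SAP has no action rule for blood pressure.

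On adverse events, Section 15 starts from this premise: "Inasmuch as the scoring of Grades 2, 3, and 4 mention that an intervention is indicated". It then provides that "AEs with Grades 2 or 3 will be brought to the attention of a study clinician", who considers whether the participant should be discontinued. "This will be done in consultation with an investigator". For Grade 4 that passage specifies reporting to the FDA and the IRB.

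**The concern.** A safety rule should never ask for less action as the reading gets worse. Here the evaluation band stops short of 180 and 110, and the discontinuation band starts above them. Followed literally, a participant at 180/90 or 150/110 gets neither the clinician's symptom check with the investigator's decision nor discontinuation. One unit lower gets the first and one unit higher gets the second. What is at stake is participant safety and consistent handling from visit to visit, not the analysis.

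The Grade 4 wording is a secondary matter of the same kind. The stated reason for a discontinuation review covers Grades 2 to 4, but the review itself names only Grades 2 and 3, so the most serious grade is left out.

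**Working it through.** **Inputs**, all from Protocol Section 15, with systolic S and diastolic D in mmHg:

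- Stop if S > 180 or D > 110 (the same in the list and the paragraph).
- Evaluate if 160 ≤ S < 180 or 100 ≤ D < 110.
- Otherwise no blood-pressure action is stated.

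Where both tiers apply, stopping is taken to override evaluation. The protocol does not say so; this is an assumption.

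**Step 1. Apply the rules as written and under each repair.**

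| Reading | As written | Evaluation closed at ≤ 180, ≤ 110 | Stopping opened at ≥ 180, ≥ 110 |
|---|---|---|---|
| 179/90 | evaluate | evaluate | evaluate |
| 180/90 | none | evaluate | stop |
| 181/90 | stop | stop | stop |
| 150/109 | evaluate | evaluate | evaluate |
| 150/110 | none | evaluate | stop |
| 150/111 | stop | stop | stop |
| 180/110 | none | evaluate | stop |
| 180/105 | evaluate | evaluate | stop |
| 170/110 | evaluate | evaluate | stop |

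**Step 2. Find the extent of the gap.** Take integer pairs with S from 120 to 220, D from 60 to 130 and S > D. Call a pair elevated if S ≥ 160 or D ≥ 100. The elevated pairs with no action are:

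- S = 180 with D from 60 to 99: 40 pairs
- D = 110 with S from 120 to 159: 40 pairs
- 180/110: 1 pair

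The total is 40 + 40 + 1 = 81, and every one has S = 180 or D = 110. The count depends on the grid chosen; the pattern does not. Readings such as 180/105 and 170/110 are outside the gap because the other component brings them into evaluation.

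**Step 3. Count what each repair does to readings that already have a rule.**

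- Closing the evaluation band: 0 readings change.
- Opening the stopping rule: S = 180 with D from 100 to 109 (10 readings) and D = 110 with S from 160 to 179 (20 readings) move from evaluation to stopping, 10 + 20 = 30 in all. These are possible readings, not expected participants.

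**Step 4. Ask whether the values can occur.** The numeric entry limits admit up to 170/100, which is 180 − 170 = 10 mmHg below the systolic gap and 110 − 100 = 10 mmHg below the diastolic gap. Protocol Section 9 has blood pressure measured before and after each cold-pressor immersion, and vital signs at eight time points on the driving day (Table 3). The documents give no blood-pressure distribution, so no frequency can be stated.

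**Step 5. Check the Grade 4 routing.** Section 15 does send solicited responses of Grade 2, 3 or 4 to a clinician. In Section 9 a clinician completes the Adverse Events Form, and in Section 15 the investigator judges relatedness for Grades 1 to 4. So Grade 4 events do reach a clinician. What is missing is the explicit discontinuation review with investigator consultation, mainly for Grade 4 events outside the solicited items.

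**The case against.** The strongest reply is that this is a one-value drafting slip that no sensible clinician would read as an instruction to do nothing, since the tiers on both sides require action. The stopping list is worded as inclusive rather than exhaustive. Several symptoms that the missed evaluation would look for have their own routes: an irregular pulse ends participation, shortness of breath is evaluated, and confusion is a solicited item. Uncontrolled hypertension and significant cardiovascular disease are excluded at entry, and Section 14 lists low rather than high blood pressure as an expected effect. The documents also do not show which tier was meant to include 180 and 110, so a preferred repair is the reviewer's choice. The Grade 4 point is separate and largely covered by other provisions.

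Much of this is fair, and it limits the size of the point. In practice the gap concerns mainly a participant without symptoms at one of two exact values. The choice of tier is clinical. The Grade 4 gap is narrow.

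It does not remove the gap. The other routes depend on symptoms or grades, whereas a blood-pressure threshold exists so that the reading itself prompts the search for symptoms. Lost characters are an unlikely explanation: the strict sign appears in both the list and the paragraph, and the ≥ signs are intact in the same paragraph.

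**Conclusion.** The concern holds. As written, the Section 15 rules give no action at a systolic of 180 when the diastolic is below 100 or exactly 110, and none at a diastolic of 110 when the systolic is below 160 or exactly 180. This is a small error in a stated safety threshold and should be corrected. The gap follows from the inequality signs alone. The assumption that stopping overrides evaluation affects only the comparison of the two repairs. How many participants it would touch is unknown. The Grade 4 omission is real but secondary.

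**What to change.** **Preferred.** In the evaluation sentence of Protocol Section 15, change the upper limits to ≤ 180 mmHg and ≤ 110 mmHg. This costs two signs in one sentence and is preferred only because it changes least.

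**Alternative**, if the sponsor wants these values to end participation. Change discontinuation to ≥ 180 or ≥ 110 in both the list and the paragraph, four signs in all. The sponsor should acknowledge that readings such as 180/105 and 170/110 then become mandatory stops, so some participants who would have continued may be withdrawn.

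**Adverse events.** Extend the clinician's discontinuation review, with investigator consultation, to Grades 2, 3 and 4, and state that Grade 4 events are also reported to the FDA and the IRB. This is one sentence.

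None of these changes affects the planned sample size, visit schedule or analysis.

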6.2 The information included in closed report

The data will be presented by blinded arms (arm X, arm Y, and arm Z), except for a notice of aggregate. The measures will be tabulated and summarized in aggregate form or by treatment arm using Mean (SD), N (%), and Median (IQR), as appropriate. The items with an asterisk (*) will be compared between arms. Kruskal-Wallis test and Fisher's Exact test will be used to compare numeric and categorical variables, respectively.

- A. *Outline of the study design:* 1) aims, 2) design summary, 3) database freezing date, 4) confidentiality statement
- B. *Enrollment and study status:* the number of 1) screened subjects (aggregate); 2) exclusion and the reasons (aggregate); 3) enrolled subjects and projected enrollment (graph of enrollment by month) (aggregate); 4) subjects completing the entire study; 5) *withdrawal from the study and the reasons; 6) missing visit(s) and the reasons.
- C. *Demographic characteristics of the cohort:* 1) age, 2) sex, 3) education, 4) Race
- D. *Baseline study relevant characteristics of the cohort*:* 1) baseline of pain intensity; 2) baseline levels of the driving performance
- E. *Baseline lab characteristics:* vital signs, e.g. heart rate and blood pressure
- F. *Safety data and study-related adverse events:* 1) type and severity (grade) of adverse events*; 2) number of adverse events; 3) number of subjects with adverse events*; 4) number of deaths related to adverse events*; 5) unanticipated problems.
- G. Protocol deviations
- H. Summary of the overall study status (closed report only)

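### The only stated adverse-event report to the FDA and IRB is keyed to Grade 4, although Grade 3 includes hospitalisation; a serious-event summary is promised to the board but neither defined nor itemised

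*Protocol*

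**What the plan says.** Protocol section 15 grades events on a four-point scale: "Adverse events will be characterized as 1 = Mild, 2 = Moderate, 3 = Severe, and 4 = Life Threatening". Two of the definitions matter here.

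- Grade 3: "Severe symptoms causing inability to perform usual social & functional activities with intervention or hospitalization indicated".
- Grade 4: "Potentially life-threatening symptoms causing inability to perform basic self-care functions with intervention indicated to prevent permanent impairment, persistent disability, or death".

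The actions then follow the grade. For the middle grades, "AEs with Grades 2 or 3 will be brought to the attention of a study clinician", who decides in consultation with an investigator whether the participant should stop taking part. For the top grade, "Grade 4 AEs will be managed by reports tendered to the FDA and the IRB within the required time limits specified by each organization". The investigator also judges relatedness to the study for every grade from 1 to 4.

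The Data and Safety Monitoring Board text in the same section says that the board's report will contain "a summary of all and serious adverse events". It also says that the board reviews safety data in real time and cumulatively, together with unanticipated problems.

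The SAP itemises the board reports in 6.1 F (open) and 6.2 F (closed, by blinded arm). Both list type and grade of adverse events, number of events, number of participants with events, deaths and unanticipated problems. The closed list ends "4) number of deaths related to adverse events*; 5) unanticipated problems", where the asterisk marks a comparison between arms. SAP 3.1 compares each participant's maximal grade across arms by a Kruskal-Wallis test. It also compares the proportion with *severe* events, a word it explains by the effect on study treatment.

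**The concern.** Severity and seriousness are different attributes. Severity describes how intense an event is; seriousness describes its outcome, such as death, admission to hospital or lasting disability. The protocol's stated rule for outside reporting uses severity alone, and its own definitions show the mismatch, because an event that calls for hospitalisation can sit one grade below the trigger.

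This is an IND trial of a product used at home for eight weeks. Section 15 itself foresees transfer to the emergency department for pulse, blood pressure or breathing findings, and attaches no external report to such a transfer. Whether a report is made under the written rule therefore depends on the grade assigned afterwards.

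The second issue is alignment. The protocol promises the board a serious-event summary. A statistician who builds the board tables from the SAP lists would not produce one, and would find no definition of *serious* to work from.

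**Working it through.** No sample size, rate or error level enters this point, so there is nothing to compute. The check sets the grade table, the action rules and the SAP lists side by side.

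| Event | Place on the 1-4 scale | Stated action (Protocol 15) | Stated FDA/IRB report | Where it appears in SAP 6.1 F / 6.2 F |
|---|---|---|---|---|
| Hospitalisation indicated, usual activities not possible | Grade 3 | Study clinician, with an investigator | None stated | Type and grade, event counts |
| Potentially life-threatening | Grade 4 | FDA and IRB reports | Yes | Type and grade, event counts |
| Death, coded as Grade 4 | Grade 4 by convention | As Grade 4 | Yes | Grade tables; death line if related to an adverse event |
| Death, not graded | None | None stated | None stated | Death line if related to an adverse event |

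1. **External report.** The table has one stated trigger, Grade 4. No other supplied text gives an FDA or IRB reporting rule for adverse events. Grade 3 covers intervention or hospitalisation, so only some Grade 3 events are hospitalisations; those are the ones affected.

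2. **Death.** The Grade 4 definition mentions death only as something that intervention is meant to prevent. The scale does not say how a fatal event is recorded. For SAP 3.1 there are two possible results. Coded as 4, a death ties with a survived life-threatening event in the rank test. Left ungraded, the participant enters with the highest grade of any other event, or with none. The SAP does not choose between them.

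3. **The word *serious*.** Protocol 15 uses it for the board report without a definition in the supplied text. SAP 6.1 F and 6.2 F do not use it. SAP 3.1 uses *severe*, explained by a consequence for treatment, which matches neither Grade 3 (defined by symptoms and function) nor the protocol's *serious*. Three safety categories are thus in play, and no text links them.

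4. **Deaths in the board lists.** The line counts deaths related to adverse events. Whether any other death is counted is not stated.

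5. **What does reach the board.** A Grade 3 hospitalisation appears by type and grade, an adverse-event-related death has its own line, and unanticipated problems are listed. What is missing is the flag that an event was serious.

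**The case against.** The strongest reply is that the protocol says Grade 4 events will be reported, not that Grade 3 events will not be. The FDA and the IRB have their own requirements, and the Adverse Events Form (Appendix 30), which was not supplied, may hold a seriousness field. A fatal event would ordinarily have met the Grade 4 threshold and would be reported on that footing. The board text requires a serious-event summary, and the SAP's shorter list does not cancel it.

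Much of this stands, and it rules out several stronger readings that a reader might infer:

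- *That serious events can escape both the regulators and the board.* The documents do not support this. The board has real-time safety data and a serious-event summary under the protocol, and grade, death and unanticipated-problem lines under the SAP.
- *That no Grade 3 hospitalisation would be reported externally.* Silence in the rule is not a reporting rate of zero.
- *That the board would wait up to six months to see such an event.* The six-month cycle in SAP section 6 is for progress reports; the protocol separately gives the board real-time data.
- *That the board cannot recommend stopping.* Its stated conclusion is a "recommendation as to whether the study should continue or be modified", and advice on whether to continue includes advice not to.
- *That every death falls outside the trigger.* A death may be coded as Grade 4; the text simply does not say so.

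What does not stand is that the rule is therefore adequate. A field on a form would not change the reporting rule in section 15, and site staff work from the rule that is written.

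**Conclusion.** The point holds in a limited form. Protocol section 15 ties its only stated FDA/IRB adverse-event report to Grade 4, while its own Grade 3 takes in events with hospitalisation indicated and receives internal review only. The scale has no explicit place for a fatal outcome. Separately, the SAP's board lists omit the serious-event summary that the protocol promises, count only deaths related to adverse events, and sit beside a third term, *severe*, with a different meaning.

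The size can be stated only by category: Grade 3 hospitalisations, and deaths if they are not coded as Grade 4. The documents give no rates for these events, so no number is projected for the 120 participants. The primary analysis and its power are not affected; the safety comparison in SAP 3.1 is affected only in how a death would be ranked.

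The conclusion rests on the text supplied. Appendices 29 and 30 were not available, and a definition of *serious* could stand there.

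**What to change.** 1. **Protocol 15, grading and action text.** Define a serious adverse event by outcome: death, life-threatening event, hospitalisation or persistent disability. Trigger FDA and IRB reporting by seriousness as well as by Grade 4. Use the relatedness judgement that the section already requires and each body's own time limits, so that an unrelated planned admission does not automatically generate a report.
2. **Protocol 15 and SAP 3.1.** State how a fatal event is coded, so that the maximal-grade comparison has a defined value for it.
3. **SAP 6.1 F and 6.2 F.** Add the number of participants with serious adverse events, compared by arm in the closed report, to match the summary promised in the protocol. Count all deaths, with those related to adverse events shown as a subset.
4. **SAP 3.1.** Align the *severe* category with the protocol's terms: either call it events leading to the end of study treatment, or use the grade or the new definition of *serious*.

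The cost is a few sentences in each document, added table rows, and a seriousness field on the event form if there is none. The downside is somewhat more reporting work; how much cannot be estimated from the documents.
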